Protocol Summary and Statistical Analysis Plan

Does inpatient enrollment into a patient communication app (Patient Gateway) result in improved follow-up and survey completion rates after orthopaedic trauma?

NCT2017P001594

Version Date 03/07/2018

**PARTNERS HUMAN RESEARCH COMMITTEE
PROTOCOL SUMMARY**

Answer all questions accurately and completely in order to provide the PHRC with the relevant information to assess the risk-benefit ratio for the study. Do not leave sections blank.

PRINCIPAL/OVERALL INVESTIGATOR

[name], MPH, FRCSC

PROTOCOL TITLE

Does inpatient enrollment into a patient communication app (Patient Gateway) result in improved follow-up and survey completion rates after orthopaedic trauma?

FUNDING

Department Funding

VERSION DATE

3/7/2018

SPECIFIC AIMS

Concisely state the objectives of the study and the hypothesis being tested.

This study aims to:

1. To determine if inpatient enrollment into a patient communication app (Patient Gateway) improves clinic follow-up of orthopaedic trauma patients.
2. To determine if inpatient enrollment into a patient communication app (Patient Gateway) improves survey completion rates after orthopedic trauma.

BACKGROUND AND SIGNIFICANCE

Provide a brief paragraph summarizing prior experience important for understanding the proposed study and procedures.

Follow-up in trauma is historically poor. As a result, outcomes from trauma are difficult to collect via surveys and are often significantly influenced by selection bias. Patient interaction apps like Patient Gateway are thought to facilitate greater participant involvement and adherence to treatment regimens. We explored if inpatient enrollment into Patient Gateway would improve clinic follow-up rates. Increasing follow-up rates could improve the quality of care delivered.

In addition, self-administered survey questionnaires are an important data collection tool in clinical practice, public health research and epidemiology. However, survey completion rates are typically poor in orthopaedic trauma.

With the evaluation of modern technology, electronic applications are being increasingly used in both hospital and personal settings. In our outpatient clinic, questionnaires to measure outcomes and monitor quality of care are

administered by staff members using hospital owned tablet devices. Recently, applications to complete these surveys on personal devices have been developed.

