In a recent Cochrane review on the comparison of self-administered survey questionnaire responses collected using mobile apps versus other methods it was concluded that there are no data available on response rates. We will attempt to address this question.

RESEARCH DESIGN AND METHODS

Briefly describe study design and anticipated enrollment, i.e., number of subjects to be enrolled by researchers study-wide and by Partners researchers. Provide a brief summary of the eligibility criteria (for example, age range, gender, medical condition). Include any local site restrictions, for example, “Enrollment at Partners will be limited to adults although the sponsor’s protocol is open to both children and adults.”

All Patient Gateway naïve patients aged 18 years or older able to consent for themselves, admitted to the hospital for an orthopaedic condition with the need for outpatient follow-up and access to the internet or a smartphone will be invited to participate in this study. Exclusion criteria will be patients unable to consent for themselves, inability to communicate in English, and no possession of a smartphone.

We will collect 240 patients; 120 in each group. Existing follow-up is assumed to be close to 70%, to detect a 15% difference at 95% CI, N=240.

Briefly describe study procedures. Include any local site restrictions, for example, “Subjects enrolled at Partners will not participate in the pharmacokinetic portion of the study.” Describe study endpoints.

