Eligible patients will be randomized into two groups; one group that is enrolled while an inpatient and another group that is just provided information about how to enroll. All patients eligible for participation will be approached during their hospital stay and asked for consent. Patients will be cluster randomized by week and after consenting, they will be assigned to the treatment arm randomized to that specific week. For intervention group, an explanation on the app will be provided by a trained research staff member and they will be fully enrolled in the app in the presence of this research staff member. In the period between hospital discharge and follow-up, patients using the Gateway app will be requested to fill out a survey on their personal device and will receive a notification of their upcoming appointment. We will monitor when patients return to clinic for their first, 90-day, and 1-year follow-up outpatient appointments. At 90 day and 1 year follow-up outpatient appointments, patients from both groups will be invited to complete a survey on a hospital owned tablet device per standard clinic protocol. In addition to the standard survey, two brief questionnaires on satisfaction with the electronic application and satisfaction with overall care

will be provided at the end of the regular survey (if already completed over the app; just the satisfaction questions will be administered).

Descriptive statistics will be used for demographic data. Logistic regression will be used for binary outcome data.

For studies involving treatment or diagnosis, provide information about standard of care at Partners (e.g., BWH, MGH) and indicate how the study procedures differ from standard care. Provide information on available alternative treatments, procedures, or methods of diagnosis.

Not applicable as this study does not alter treatment or diagnosis in any way.

Describe how risks to subjects are minimized, for example, by using procedures which are consistent with sound research design and which do not unnecessarily expose subjects to risk or by using procedures already being performed on the subject for diagnostic or treatment purposes.

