When specimens or data collected by research collaborators outside Partners will be sent to Partners investigators, indicate from where the specimens/data will be obtained and whether the specimens/data will contain identifiers that could be used by Partners investigators to link the specimens/data to individual subjects. When appropriate, submit documentation of IRB approval and a copy of the IRB-approved consent form from the institution where the specimens/data were collected.

No specimens/data will be received from sites outside of partners for future use.

Statistical analysis, study size

Descriptive statistics were used for demographic data. Differences between groups were assessed using the chi-square or Fisher's exact test for categorical variables and the t-test and/or analysis of variance (ANOVA) for continuous variables. Demographic or treatment factors associated with improved follow-up or EPP use were assessed using forward stepwise logistic regression modeling to avoid overfitting. We also performed a sub-group analysis assessing the effect of patient race and average median income. A robustness analysis exploring the likelihood of enrolling in an EPP or completing follow-up in all patients was also performed. Significance was set at $P < 0.05$. Stata software, version 14 (StataCorp), was used for all analyses.

An a priori power analysis was completed to determine sample size, we assumed an existing follow-up rate of 70%, and to detect an ~10% difference in follow-up with an alpha of 0.05, we calculated an approximate sample size of 200 patients distributed equally between both groups.

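### The stepwise factor models, EPP-use model, race and income sub-groups and robustness analysis are not shown to be pre-specified, yet share one P < 0.05 with the comparison of the randomised arms

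*Combined protocol and SAP*

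**What the plan says.** The combined document is titled as a protocol summary and statistical analysis plan and carries one date: "Version Date 03/07/2018". Under Research Design and Methods it looks ahead. On recruitment it says "We will collect 240 patients; 120 in each group". The whole of its analysis plan is two sentences: "Descriptive statistics will be used for demographic data" and "Logistic regression will be used for binary outcome data". Specific Aims gives two questions, one on clinic follow-up and one on survey completion.

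The last section, Statistical analysis, study size, is in the past tense and goes further:

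- Factor models: "Demographic or treatment factors associated with improved follow-up or EPP use were assessed using forward stepwise logistic regression modeling to avoid overfitting".
- Sub-groups: "We also performed a sub-group analysis assessing the effect of patient race and average median income".
- Robustness: "A robustness analysis exploring the likelihood of enrolling in an EPP or completing follow-up in all patients was also performed".
- Threshold: "Significance was set at $P < 0.05", with nothing to limit it to particular analyses.

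This section has no separate date. It labels no analysis confirmatory, exploratory or post hoc, and it gives no rule for multiple testing.

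**The concern.** Readers use a document labelled as an SAP to tell planned results from data-driven ones. Here the label covers a search for predictive factors, an outcome (EPP use) that is not among the aims, two sub-group factors and a robustness analysis. Nothing in the document shows that any of them was chosen before outcomes were seen. With one threshold for everything, a race, income or factor result at P = 0.04 could be declared significant with the same standing as the comparison of the randomised arms.

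The matter at stake is how these added results are read. The validity of the comparison between arms is not in question here, nor is the merit of stepwise selection as a method.

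**Working it through.** **Step 1. Set the two parts side by side.**

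| Item | Protocol body (Specific Aims; Research Design and Methods) | Statistical analysis, study size |
|---|---|---|
| Descriptive statistics | Planned, future tense | Reported, past tense |
| Logistic regression | Planned for binary outcomes; no covariates or selection rule named | Forward stepwise selection of factors |
| Clinic follow-up | Aim 1 | Addressed |
| Survey completion | Aim 2 | Not mentioned |
| EPP use | Not an aim; the abbreviation does not appear | Modelled as an outcome |
| Race and income sub-groups | Not named | Reported as done |
| Robustness analysis | Not named | Reported as done |
| Design basis | 70% follow-up, 15% difference, 240 patients | 70% follow-up, about 10% difference, about 200 patients |

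Outside the statistical section, race appears only in the recruitment statement under Equitable Selection of Subjects. Income appears nowhere else.

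**Step 2. Ask whether the statistical section can be taken as the plan behind the protocol.** It omits one of the two aims, adds an outcome and uses a different term for the app. It also rests on a different design. To check the stated sizes I used the pooled normal approximation, two-sided 5%, with 80% power assumed because neither section states power:

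n per arm = [1.960·√(2·p̄·(1−p̄)) + 0.842·√(p₁(1−p₁) + p₂(1−p₂))]² / (p₂−p₁)²

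- 70% vs 85%: p̄ = 0.775, giving [1.960·√0.34875 + 0.842·√0.3375]² / 0.0225, which rounds up to 121 per arm, 242 in total. The protocol's 240 is reproduced.
- 70% vs 80%: p̄ = 0.75, giving [1.960·√0.375 + 0.842·√0.37]² / 0.01, which rounds up to 294 per arm, 588 in total. The statistical section's figure of about 200 is not reproduced. At 100 per arm, two-sided power is about 37%.

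The sample-size conflict is a separate matter. It is used here only because it suggests that the two parts were written separately.

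**Step 3. Illustrate what a shared threshold allows.** The documents do not give the number of tests: candidate factors are not listed, and the outcomes for the race and income analysis are not stated. For k independent null tests at 0.05, the chance of at least one P < 0.05 is 1 − 0.95^k:

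- k = 3: 1 − 0.857 = 14.3%
- k = 4: 1 − 0.815 = 18.5%
- k = 8: 1 − 0.663 = 33.7%
- k = 10: 1 − 0.599 = 40.1%

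Four tests would arise if race and income were each examined for follow-up and for EPP use. Eight would arise if follow-up were taken at each of the three monitored visits, plus EPP use. Both counts are assumptions. Attendance of the same patients at successive visits is likely to be correlated, and race and income may be too. Positive correlation lowers these figures, towards 5% in the limit of perfectly correlated tests.

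**The case against.** A reader might infer from the past tense that the analyses were chosen after the outcomes were seen. The documents do not support that. The same section puts the descriptive statistics, which the protocol did plan, in the past tense, and does the same with a power analysis that it calls a priori. Background and Significance also has a past-tense sentence about what the study explored. Tense shows when text was written, not when an analysis was chosen.

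A reader might also infer that the trial had not enrolled at the version date. No enrolment status is stated; the protocol is only written as if recruitment lay ahead.

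Three further objections have weight:

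- The protocol's logistic regression sentence is not restricted to the arm comparison, so it could cover some modelling of follow-up or EPP use. What it does not name is the stepwise selection, the search for predictors, EPP use as an outcome, the sub-groups and the robustness analysis.
- The statistical section never calls these analyses confirmatory, and its wording for the robustness analysis is itself exploratory in tone. The risk of misreading comes mainly from the SAP title and the undivided threshold.
- It would be too strong to say that there is no error control. A nominal 5% per test is stated; family-wise control is absent.

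These points limit the conclusion to absence of evidence for pre-specification. They do not supply that evidence.

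**Conclusion.** The point holds in this limited form. The documents do not show that the stepwise factor models, the EPP-use model, the race and income sub-groups or the robustness analysis were pre-specified, and they apply one P < 0.05 to all of them. Whether they were in fact post hoc cannot be settled from the documents.

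No false-positive rate can be assigned to this trial. The range of 14% to 40% for 3 to 10 tests assumes independence and test counts that the plan does not give, so it is an illustration and, for those counts, overstates the risk if the tests are positively correlated. The conclusion does not depend on it; it rests on the comparison of sections in step 1.

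The effect is confined to the interpretation of the added results. The correction is worth making because it is cheap and changes what the trial may claim from them.

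**What to change.** In Statistical analysis, study size:

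1. Name the comparison of the randomised arms on the two stated aims, clinic follow-up and survey completion, as the confirmatory analysis, and reserve P < 0.05 for it. This must be written in as a new statement: the protocol's logistic regression sentence does not itself specify arm, outcome or visit.
2. Label the stepwise factor models, the EPP-use model, the race and income sub-groups and the robustness analysis as *not specified in the protocol; exploratory*. Report them as estimates with 95% CIs and make no significance claims.
3. If a plan dated before outcome review contains any of these analyses, cite it with its date and exempt those analyses from the label.

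The cost is wording in the SAP and the report; no analysis has to be dropped. The downside is that factor, EPP-use, sub-group and robustness results can no longer be claimed as significant findings. The change does not settle multiplicity across the two aims and the several visits, or how the arm comparison allows for randomisation by week. Those need their own statements.

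### The two sample-size statements conflict: from the same 70% baseline, 240 patients are paired with 15 points and about 200 with 10 points, and 200 patients give only about 37% power for 10 points

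*Combined protocol and SAP*

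**What the plan says.** Research Design and Methods sets the target: "We will collect 240 patients; 120 in each group". The justification follows: "Existing follow-up is assumed to be close to 70%, to detect a 15% difference at 95% CI, N=240".

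The closing section, Statistical analysis, study size, gives a different calculation and presents it as prospective: "An a priori power analysis was completed to determine sample size, we assumed an existing follow-up rate of 70" per cent. It continues: "to detect an ~10% difference in follow-up with an alpha of 0.05, we calculated an approximate sample size of 200 patients", split evenly between the arms.

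Neither statement gives the power, says whether the test is one- or two-sided, or says whether the difference is absolute or relative. Neither mentions an allowance for the allocation method, although the study procedures state: "Patients will be cluster randomized by week".

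**The concern.** Both calculations start from 70% follow-up and, reading the 95% confidence interval in the first as alpha 0.05, both use the same significance level. Yet the smaller difference goes with the smaller sample. That is impossible unless power or sidedness also changed, and no such change is stated.

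Clinic follow-up is the first specific aim, so this is the calculation on which the trial's sensitivity is judged. As the document stands, a reader cannot tell whether the target was 200 or 240, or whether the design difference was 10 or 15 points. Someone reading only the closing section would reasonably infer that the trial was adequately sized for a 10-point rise. If it was not, a non-significant result could be misread as showing that inpatient enrolment does not help.

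**Working it through.** **Inputs from the document.** Baseline 70% (both sections); alpha 0.05; equal arms; 15 points with 120 per arm (Research Design and Methods); about 10 points with 100 per arm (Statistical analysis, study size).

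**Assumptions.** Two-sided test, absolute rise and 80% power, because the document states none of these. Other readings are tried below.

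**Formulas** (two proportions, pooled variance under the null). With d = p2 − p1 and p̄ the mean of p1 and p2:

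- n per arm = [z(α)·√(2p̄(1−p̄)) + z(power)·√(p1(1−p1) + p2(1−p2))]² / d²
- power = Φ{[d√n − z(α)·√(2p̄(1−p̄))] / √(p1(1−p1) + p2(1−p2))}

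**Step 1: 15 points, 240 patients.** p̄ = 0.775, so √0.34875 = 0.5906; √(0.21 + 0.1275) = 0.5809.

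- n = (1.960 × 0.5906 + 0.8416 × 0.5809)² / 0.0225 = 1.6464² / 0.0225 ≈ 120.5, so 121 per arm (242 in total).
- Power at 120 per arm is 79.8%. The planned 240 reproduces.

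**Step 2: 10 points, about 200 patients.** p̄ = 0.75, so √0.375 = 0.6124; √(0.21 + 0.16) = 0.6083.

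- n = (1.960 × 0.6124 + 0.8416 × 0.6083)² / 0.01 = 1.7122² / 0.01 ≈ 293.2, so 294 per arm (588 in total).
- Power at 100 per arm = Φ[(0.10 × 10 − 1.2002) / 0.6083] = Φ(−0.329) = 37.1%.
- The stated 200 is short by a factor of 588 / 200 = 2.94.

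**Step 3: other readings of the second statement, 100 per arm.**

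| Reading | Power | Total for 80% power |
|---|---|---|
| Two-sided, 70% vs 80% | 37.1% | 588 |
| One-sided, 70% vs 80% | 49.5% | 462 |
| Two-sided, relative rise, 70% vs 77% | 20.0% | 1,246 |
| Two-sided, fall, 70% vs 60% | 31.6% | 712 |

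The choice of test does not change the picture. Exact enumeration for 70% versus 80% at 100 per arm gives 37.1% for the uncorrected chi-square test and 31.3% for Fisher's exact test, the two tests named in that section. About 200 appears only on unconventional readings: a one-sided test at 50% power (204 in total), or a one-sample test of 80% against a fixed 70% at two-sided 90% power (about 199). The latter contradicts the two equal arms described.

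**Step 4: what each size can detect (two-sided 0.05).**

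| | 200 patients | 240 patients |
|---|---|---|
| Power for 10 points | 37.1% | 43.2% |
| Chance of missing 10 points | 62.9% | 56.8% |
| Power for 15 points | 72.2% | 79.8% |
| Rise detectable at 80% power | 16.3 points | 15.0 points |

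**Step 5: randomisation by week.** The document gives neither an intraclass correlation nor a weekly number of patients. Purely as an illustration, 5 patients per week and a correlation of 0.01 to 0.05 give a design effect of 1 + 4 × 0.01 = 1.04 to 1 + 4 × 0.05 = 1.20. Power then becomes 78% to 72% for 240 patients and 15 points, and 36% to 32% for 200 patients and 10 points. The reduction arises only if the correlation is positive, and the conflict in Steps 1 and 2 does not depend on it.

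**The case against.** The 37% is conditional: the document states neither power, sidedness nor the type of difference, and about 200 does match a one-sided test at 50% power. This is correct, but it does not rescue the statement. No conventional combination brings 200 near adequate power for 10 points, and the conflict between the sections stands without any assumed power.

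A better objection is that 200 may be a genuine calculation with the wrong difference beside it. One-sided, 70% versus 85% needs 95 per arm (190 in total) for 80% power, and 100 per arm gives 81.9%. That would make the 10% the slip rather than the 200. It does not reconcile the text as written, and a plain P < 0.05 with chi-square and Fisher's tests reads most naturally as two-sided. It does mean the sponsor must confirm sidedness before replacement wording is settled.

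Finally, Research Design and Methods is the forward-looking statement and is sound at about 80% power, whereas the closing section is in the past tense. If 240 governed, the error sits in one retrospective sentence. But that section calls its calculation a priori and is the only detailed statistical text, so a reader cannot know which target applied.

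**Conclusion.** The concern holds. The two statements cannot both be right at the same power and sidedness, and the pairing of about 200 patients with 10 points fails on every conventional reading. With a two-sided 0.05 test and an absolute rise from 70%, power for 10 points is about 37% at 200 patients and 43% at 240. One-sided, it is about 50% and 56%. Whichever size governed, a non-significant result should not by itself be read as evidence against a 10-point benefit. These figures make no allowance for randomisation by week and would be lower with any positive correlation within weeks.

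**What to change.** The sponsor should check its records to establish whether 200 or 240 governed, and whether the test was meant to be two-sided. It should then remove the claim that about 200 patients suffice for 10 points and give one calculation, identical in both sections, with power, sidedness and the type of difference stated:

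- **If 240 governs:** 120 per arm, 70% versus 85%, two-sided alpha 0.05, about 80% power.
- **If 200 governs:** 100 per arm, an absolute rise of about 16 points from 70%, two-sided alpha 0.05, 80% power.

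If the records show a one-sided design, the rise detectable at 80% power is 13.5 points at 120 per arm or 14.6 at 100 per arm, and the text should say so.

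Under the two-sided design, add a sentence to this effect, keeping only the power for the governing size: *These figures are before any allowance for randomisation by week. Power to detect a 10-point benefit is low (43% at 240 patients; 37% at 200), so a non-significant result alone is not evidence against one.*

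The cost is wording and a records check. No patients are added, but the stated detectable difference becomes less favourable, at 15 to 16 points instead of about 10. Keeping 10 points at 80% power would take about 588 patients before clustering, which is not proposed here.
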